## 8.7 Unscheduled Visits

A single patient-level data listing will be provided to disclose the details of all assessments performed during unscheduled visits, including assessments intended to correspond to nominal visits but incidentally performed out-of-window.

# 9 EFFICACY ANALYSES

All efficacy analyses will be performed using data collected from the Safety Population. For select hematology measures, however, analyses will be additionally performed using data from the Evaluable Population. Results will be presented in tables and figures and derived for individual patient cohorts (dose levels), as well as all patients combined (see **Appendix 2** for proposed data summaries). Data describing individual patients will be disclosed in data listings.

## 9.1 Clinical Laboratory Assessments

Laboratory assessments to be used in efficacy analyses will include select hematology measures (hemoglobin, hematocrit, and platelets). Within a single table for each of 2 populations (Safety and Evaluable), the numbers and percentages of patients will be presented by categorized patterns of post-infusion change, including clinical improvement, stability/no change, and clinical worsening, for each of 2 post-infusion timeframes (infusion through the 24-hour post-infusion visit and infusion through the Day-6 visit). For each patient, categorization will require consideration of all measurements recorded across all time-points within the timeframe. For each hematology measure, clinical improvement and worsening will be defined as shown below. The category of stability/no change will apply by default when, for an individual patient, neither improved nor worsened conditions have been observed following infusion. When both improved conditions and worsened conditions have been distinctly observed at different time-points, the patient will fall into the category of clinical improvement.

Clinical improvement will be defined by:

- Hemoglobin increase of 1 g/dL
- Hematocrit increase of 3%
- Platelet count increase of 5,000/ $\mu$ L

Clinical worsening will be defined by:

- Hemoglobin decrease of 1 g/dL
- Hematocrit decrease of 3%
- Platelet count decrease of 5,000/ $\mu$ L

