Routine Chemistry: Na, K, Cl, CO2, Glucose, BUN, Creatinine, Albumin, Total Bili, Ca, AST, Alkaline Phosphatase, ALT, GGT, LDH, Total Cholesterol, Total Protein			X		X	X					
Special Chemistry hsTroponin I or T Assay			X		X	X					
Draw archive sample	X									X	

Evaluation	Initial Screen	Rescreen (if applicable  )	Day 1  Base Line -2 hr pre-infusion	1 hr post infusion ± 15min	6 hr post -1 or +2 hr	Day 2 24 hr post ± 3 hr	If hospitalized			Day 6 (+ 4 days)	Day 30 (+2 days) (by phone)								
							Day 3	Day 4	Day 5										
 Rescreening performed on those patients who passed eligibility criteria, were not actively bleeding at time of initial screen, and started bleeding within 4 weeks. Patients who were initially screened within 4 days (+6 hrs) do not need to be re-screened except for WHO bleeding assessment and CBC.																			
 Baseline may occur on the same day (within 24 hours) as either Initial Screen or Rescreen. The WHO assessment, CBC and coagulation must be collected at baseline, not more than 2 hours prior to infusion. Red cell transfusion must be specifically related to treatment of bleeding within 24 hours of onset of bleeding.																			
 Chart review for SAEs (only) needs to include data from day 1 though Day 30 (+2 days). Phone call with patient is to confirm if the patient had an SAE or required emergency medical care at an outside facility.																			
 Complete physical exam to include height, weight, general assessment of health by history and medical exam including neurological exam. History to include previous transfusion with red blood cells, plasma and/or platelets.																			
 Abbreviated Physical Exam to include general appearance, cardiovascular, respiratory, extremities, abdomen and head and neck.																			
 In the event of the transfusion of a blood component after infusion of Thrombosomes on Days 1-6, CBC results are required from a sample collected within 8 hours or less prior to the transfusion and within 1-hour (+30 min) post transfusion.																			
 Daily CBC required, but ALL CBC data for each patient during the hospitalization phase through Day 6 must be collected and entered into the database.																			
 If TEG or ROTEM testing is available, include samples for the record.																			

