### 2.2.2 Secondary Endpoints

Multiple secondary endpoints will be quantified per patient cohort (i.e., by dose level), as well as overall (i.e., across all 3 dose levels):

- Number and percentage of patients who, from baseline to post-baseline time-points, show either stability (i.e., no change) or an intermittent or sustained change toward clinical improvement in hematology measures, with or without reaching normal levels.
- Number and percentage of patients who receive transfused blood products following infusion.
- Statistics describing central tendency and variability in the numbers of units of blood products transfused following infusion.

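### SAP 9.1 classifies patients from however many blood counts they happen to have, so through Day 6 the improved, stable and worsened percentages depend on inpatient share

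*SAP*

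**What the plan says.** SAP 9.1 sorts each patient into improvement, stability or worsening for hemoglobin, hematocrit and platelets. It does so over two timeframes: infusion to the 24-hour visit, and infusion to the Day-6 visit. The thresholds for improvement are "Hemoglobin increase of 1 g/dL", "Hematocrit increase of 3" (percent) and "Platelet count increase of 5,000" (per µL); worsening uses the same amounts downward.

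Three rules decide the category:

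- The input is open-ended: "categorization will require consideration of all measurements recorded across all time-points within the timeframe".
- Stability is a default, used only when "neither improved nor worsened conditions have been observed following infusion".
- Mixed patterns go one way: "When both improved conditions and worsened conditions have been distinctly observed at different time-points, the patient will fall into the category of clinical improvement".

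SAP 2.2.2 frames the secondary endpoint as the percentage of patients who are either stable or show "an intermittent or sustained change toward clinical improvement in hematology measures". SAP 6.3 sets baseline as the last value before infusion.

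On the number of counts, Protocol Table 4 and SAP Table 2 schedule a CBC at 1, 6 and 24 hours and on Day 6 for everyone. They add at least a daily CBC on Days 3 to 5 for hospitalized patients only. Inclusion criterion 5 admits patients who are not hospitalized. Footnote 7 to Protocol Table 4 adds that "ALL CBC data for each patient during the hospitalization phase through Day 6 must be collected", and footnote 6 requires counts before and after any transfusion on Days 1 to 6. SAP 6.2 leaves open whether unscheduled data enter the summaries.

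**The concern.** SAP 9.1 does not say in so many words that any single count suffices. It follows from the default rule for stability, the tie rule and the endpoint's acceptance of a temporary change. No confirmation is required, no set of visits is fixed, and nothing allows for the number of counts. The chance that at least one of several readings lies a fixed distance from a shared baseline rises with the number of readings, even when nothing is happening.

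Inpatients have more scheduled readings than outpatients in the Day-6 timeframe. Cohorts are filled in order of enrollment (SAP 3.1), and SAP 6.5 plans no stratification or covariate adjustment, so nothing balances or corrects for inpatient share. SAP 2.1.2 treats these patterns as preliminary indicators of efficacy, and the table is reported by dose cohort. A difference between cohorts could therefore reflect how often blood was drawn.

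**Working it through.** The plan gives no expected rate for this endpoint, so there is no figure of its own to reproduce.

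**Inputs from the documents.** Scheduled post-infusion counts through Day 6: outpatient 1 h, 6 h, 24 h, Day 6, so k = 4; inpatient 4 + Days 3, 4 and 5, so k = 7 at least. Through 24 h: k = 3 for everyone. Thresholds c: 1 g/dL, 3 hematocrit points, 5,000/µL. One shared baseline value.

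**Assumed.** Normal readings with no true change and within-patient SD s, which the documents do not give. Readings are independent in the first calculation. A change of exactly c counts as crossing.

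**Formulas.** With φ and Φ the standard normal density and distribution function, r = c/s and x the standardized baseline:

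- P(improved) = ∫ φ(x)[1 − Φ(x + r)^k] dx
- P(worsened), with improvement taking priority = ∫ φ(x){Φ(x + r)^k − [Φ(x + r) − Φ(x − r)]^k} dx
- P(stable) = 1 − P(improved) − P(worsened)
- P(stable or improved), the SAP 2.2.2 percentage = 1 − P(worsened)

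**Results, 4 counts → 7 counts (%):**

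| Measure and assumed SD | Improved | Stable | Worsened | Stable or improved |
|---|---|---|---|---|
| Hb 0.3 g/dL | 3.1 → 4.8 | 93.8 → 90.4 | 3.1 → 4.8 | 96.9 → 95.2 |
| Hb 0.4 g/dL | 11.5 → 16.5 | 77.1 → 67.1 | 11.4 → 16.4 | 88.6 → 83.6 |
| Hb 0.5 g/dL | 21.2 → 28.9 | 57.9 → 43.3 | 20.9 → 27.8 | 79.1 → 72.2 |
| Platelets 3,000/µL | 29.9 → 39.2 | 41.7 → 25.7 | 28.4 → 35.1 | 71.6 → 64.9 |
| Platelets 5,000/µL | 50.6 → 61.5 | 11.1 → 2.8 | 38.3 → 35.7 | 61.7 → 64.3 |
| Platelets 7,000/µL | 59.9 → 70.4 | 3.6 → 0.4 | 36.5 → 29.2 | 63.5 → 70.8 |

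Only the ratio c/s matters, so hematocrit at SD 1.5 points (3/1.5 = 2) gives the same row as hemoglobin at 0.5 g/dL (1/0.5 = 2).

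Improved rises and stable falls in every row. Worsened rises at the lower SDs and falls at the two highest, where the tie rule moves mixed patterns into improved. The SAP 2.2.2 percentage therefore falls with more counts at low noise and rises at high noise.

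**Correlated readings.** Readings were simulated with correlation decaying over time, for platelets at SD 4,000/µL:

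| Correlation | Improved, 4 → 7 counts (%) | Gap (points) |
|---|---|---|
| Independent | 42.5 → 53.1 | 10.6 |
| Time constant 1 day | 27.9 → 42.5 | 14.6 |
| Time constant 3 days | 19.3 → 29.2 | 9.9 |

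Correlation lowers the rates but not always the gap, because the early counts stay close to baseline while those on Days 3 to 5 do not.

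**Size per cohort.** The extreme contrast is 8 outpatients against 8 inpatients. Under independence the expected difference in patients labelled improved is 8 × (0.165 − 0.115) = 0.4 for hemoglobin at SD 0.4, and 8 × (0.392 − 0.299) = 0.7 for platelets at SD 3,000. With the 1-day time constant at SD 4,000 it is 8 × 0.146 = 1.2. A 25-point difference in inpatient share gives a quarter of these: 0.1, 0.2 and 0.3 patients.

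**The case against.** A reader might infer that the rule builds in a bias toward efficacy. The table above does not support that. At hemoglobin SDs of 0.4 to 0.5 g/dL and platelet SD 3,000/µL, extra counts move patients out of stable almost equally in both directions, and the stable-or-improved percentage of SAP 2.2.2 falls for inpatients. It rises only at larger noise.

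A reader might also apply the argument to both timeframes, or to 10 or more counts per inpatient. Through 24 hours everyone has the same three scheduled counts. Larger numbers rest on unscheduled or transfusion-related counts: the protocol requires these to be collected, SAP 9.1 appears to include them, and SAP 6.2 leaves their use in summaries open. Only 4 against 7, in the Day-6 timeframe, is secure.

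The remaining objections concern size. The SDs are assumptions. Protocol 1.9.2 describes the population as hospitalized, although criterion 5 admits others, so a large difference in inpatient share between cohorts is possible but not shown. No test is planned for this table, so type I error is not at issue. Individual hemoglobin and platelet courses appear in plots, and all three measures in a listing, so a reader of the report can look behind the percentages. All of this limits the consequence. None of it removes the dependence on sampling frequency.

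**Conclusion.** The point holds for the Day-6 timeframe. As written, SAP 9.1 makes the category depend on how many counts a patient has, and scheduled counts differ by design: 4 for outpatients, at least 7 for inpatients. That more counts raise the improved percentage and lower the stable percentage held for every SD and correlation examined. The amount, and the direction for worsened and for stable-or-improved, depend on a within-patient SD that the documents do not state.

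The consequence is that these percentages cannot be compared cleanly between cohorts with different inpatient shares. In a descriptive table of 8 patients per cohort the expected distortion is about one patient even in the extreme contrast, and much less for realistic differences in mix. It is a modest matter, worth correcting because the correction is simple.

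**What to change.** In SAP 9.1, replace the reference to all recorded measurements with the scheduled time-points every patient shares: 1, 6 and 24 hours for the first timeframe, and 1, 6 and 24 hours plus Day 6 for the second. Keep the existing thresholds. Show Days 3 to 5 and any other extra counts only in the hematology listing (16.2.6.2) and, for hemoglobin and platelets, the SAP 8.3 plots. This also settles, for this table, the question SAP 6.2 leaves open.

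Both groups then have the same chance of crossing a threshold: for platelets at SD 3,000/µL, 30% improved with no true change, whether hospitalized or not. The change equalizes that rate; it does not reduce it.

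Using the Day-6 value alone for the second timeframe would lower the rate (12% in the same case) but is not recommended. It discards three counts everyone has, conflicts with the endpoint's acceptance of an intermittent change, and leaves Safety Population patients without a Day-6 visit unclassifiable.

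The cost is SAP wording only; no visit or sample changes. Some collected inpatient counts, and any temporary change seen only on Days 3 to 5, would no longer contribute to this table.

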#### 2.1.2 Secondary Objective

The secondary objective of this study is to assess potential efficacy of Thrombosomes for managing bleeding in actively-bleeding, thrombocytopenic patients.

Efficacy will be assessed within and across 3 sequentially enrolled patient cohorts, treated, respectively, at 3 escalating dose levels (see *Primary Objective* above). Post-infusion patterns showing stability or change toward clinical improvement in hematology measures will be used as preliminary indicators of possible product efficacy in bleeding management, and patterns in the receipt of transfused blood products will also be examined.

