### **5.3 Evaluable Population**

The Evaluable Population will include all patients from the Safety Population who completed the planned Day-6 follow-up visit (on Day 6 +4 days) and, thus, were classified as "evaluable". The Evaluable Population will be used, along with the Safety Population, in select efficacy analyses supporting the Secondary Objective.

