#### **6.4 Missing Values**

For all patients enrolled and all activities and assessments performed, every effort will be made to achieve complete data collection. Imputation is not planned for missing data, other than for missing date/time values. The missing component(s) of incomplete dates (e.g. start or stop dates of TEAEs, concomitant medication use, events/conditions in medical history) will be assumed to be the most conservative value possible. For example, if the start date is missing the day value, then the first day of the month will be imputed for study day computations. If the end date is missing the day value, then the last day of the month will be imputed. A similar approach will be used for missing month and year components. For complete dates but missing start or end times, values marking the beginning of the day (00:00:00AM) or end of the day (23:59:59PM), respectively, will be imputed. Importantly, date/time imputation will be used for computational purposes only; actual data values (as they appear in the database) will be presented in all patient-level data listings. Patients who withdraw consent for study participation or are lost to follow-up will be included in data summaries and analyses to the point of last contact.

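### SAP 9.1 classes patients as stable by default, so an early exit or missing count with no recorded threshold change is reported as a favourable result, mainly in the Day-6 timeframe of the Safety Population table

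*SAP*

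**What the plan says.** SAP 9.1 classifies each patient on hemoglobin, hematocrit and platelets over two timeframes: infusion to the 24-hour visit and infusion to the Day-6 visit. For each patient, "categorization will require consideration of all measurements recorded across all time-points within the timeframe". Improvement and worsening are fixed steps up or down. For worsening these are "Hemoglobin decrease of 1 g/dL", a hematocrit fall of 3% or a platelet fall of 5,000/µL. If both directions are seen at different times, "the patient will fall into the category of clinical improvement". Everyone else is covered by this sentence: "The category of stability/no change will apply by default when, for an individual patient, neither improved nor worsened conditions have been observed following infusion".

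The SAP treats stability as a good result. Section 2.1.2 says: "Post-infusion patterns showing stability or change toward clinical improvement in hematology measures will be used as preliminary indicators of possible product efficacy". The first secondary endpoint in Section 2.2.2 counts patients who "show either stability (i.e., no change) or an intermittent or sustained change toward clinical improvement in hematology measures".

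Table 14.2.1.1 uses the Safety Population, which SAP 5.2 defines as every infused patient, however long they were followed. Table 14.2.1.2 repeats the analysis in a narrower group: "The Evaluable Population will include all patients from the Safety Population who completed the planned Day-6 follow-up visit". SAP 6.4 imputes dates and times only, and says that patients who withdraw or are "lost to follow-up will be included in data summaries and analyses to the point of last contact". SAP 6.3 sets a change from baseline to missing if either value is missing.

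**The concern.** The default depends on what has been observed, not on whether there was enough observation to see a change. Section 9.1 does not ask for a baseline value, a minimum number of post-infusion counts or a count near the end of the timeframe. It has no row for patients who cannot be assessed and no rule for death or withdrawal. A patient with flat counts to 6 or 24 hours who then leaves is therefore reported as stable through Day 6, and Section 2.2.2 counts that as favourable.

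The Evaluable table does not repair this. It removes patients without a Day-6 visit from both timeframes, including the 24-hour one. An evaluable patient who attended Day 6 but lacks counts can still fall into stability by default. For early exits with no threshold change, the reader gets one table that calls them stable and one that leaves them out. At stake are the reported favourable percentage and the informal reading of it across dose cohorts.

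**Working it through.** **No figure to reproduce.** The sample size was not statistically derived (SAP 4), and no target percentage is stated for this endpoint. The check is of the classification rule and its arithmetic.

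**Step 1: apply the rule literally.** Order: any rise at or above the threshold is improvement; otherwise any fall at or beyond it is worsening; otherwise stability. Hypothetical hemoglobin profiles, baseline 8.0 g/dL, threshold 1 g/dL, infusion-to-Day-6 timeframe:

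| Recorded values after infusion | Then | Class | Favourable under 2.2.2 |
|---|---|---|---|
| none | – | stability | yes |
| 7.9 | death | stability | yes |
| 8.1, 7.9, 7.8 (1, 6, 24 h) | withdrawal | stability | yes |
| 7.8, 6.8 | death | worsening | no |
| 8.0, 9.1, 6.5 | death | improvement | yes |

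The first three rows are the problem. The third is properly stable to 24 hours, but its class is carried to Day 6 without data. The fourth row shows that an early exit with a recorded fall is not favourable.

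**Step 2: size.** Let n be patients infused in a cohort, m those with no recorded threshold change because follow-up ended or counts are missing, and k those favourable among the other n − m.

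- As written: (k + m)/n
- Observed only: k/(n − m)
- Affected patients not counted as favourable: k/n

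As written minus not favourable is m/n, so each patient adds 1/8 = 12.5 points, or 1/10 = 10 points with 10 infused. As written minus observed only is (m/n) × [1 − k/(n − m)], which is smaller whenever k > 0.

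| n | m | k/(n − m) | As written | Observed only | Not favourable |
|---|---|---|---|---|---|
| 8 | 1 | 4/7 | 5/8 = 62.5% | 57.1% | 4/8 = 50.0% |
| 8 | 2 | 3/6 | 5/8 = 62.5% | 50.0% | 3/8 = 37.5% |
| 8 | 3 | 2/5 | 5/8 = 62.5% | 40.0% | 2/8 = 25.0% |
| 10 | 2 | 4/8 | 6/10 = 60.0% | 50.0% | 4/10 = 40.0% |

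All k and m are assumed. The n = 10 row is there because SAP 4 targets 8 evaluable patients per cohort, so exits may enlarge the Safety denominator.

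**Step 3: how many patients.** The documents give no early-exit rate. At an assumed 5% to 20%, a cohort of 8 would have 8 × 0.05 = 0.4 to 8 × 0.20 = 1.6 early exits, and only those without a recorded threshold change count towards m. Protocol 1.10.1 plans about 30 enrolled and 24 evaluable. SAP 3.1 defines enrolment as the start of infusion, but SAP 11 notes that the protocol gave no definition, so the difference of 6 is not evidence of six early exits.

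**Step 4: where it falls.** Protocol Table 4 schedules CBCs at baseline and at 1, 6 and 24 hours, so the 24-hour timeframe should be little affected. Days 3 to 5 apply only to hospitalized patients. For a discharged patient with flat counts at 24 hours, Day 6 is the only scheduled count left; other counts are required only around a transfusion.

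**The case against.** The strongest reply is that the gap is narrow and its direction is not fixed. A deteriorating patient may cross a worsening threshold before leaving, and is then classed as worsening. Because improvement overrides worsening, longer follow-up can turn worsening into improvement but never the reverse. An exit after a fall therefore locks in an unfavourable class, and truncation can also lower the favourable percentage. All of this stands. A reader might infer that neither table ever counts an early exit as unfavourable, that every early exit adds 12.5 points, or that the bias must favour the product. Section 9.1 supports none of these; the inflation is limited to exits and gaps with no recorded threshold change.

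It can also be said that a baseline CBC is required within 2 hours before infusion, that deaths, discontinuations and individual counts are listed, and that the analysis is descriptive, with no test planned and no place in the DMC tables and listings of SAP Appendix 1. This limits the consequence: type I error and power are unaffected, and these tables are not in the listed package for the escalation reviews. It does not make the percentage correct. A reader should not have to rebuild an endpoint from listings.

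The missing-change rule in SAP 6.3 does not help. Section 9.1 has no category to receive a missing change, and a patient with flat early counts has valid changes anyway.

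**Conclusion.** The point holds in a limited form. SAP 9.1 reports as stable, and SAP 2.2.2 therefore counts as favourable, any Safety Population patient with flat or absent counts who then dies, withdraws or has no later count. The effect falls mainly on the infusion-to-Day-6 timeframe of Table 14.2.1.1, and Table 14.2.1.2 hides non-completers instead of correcting for them.

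The 12.5 points per affected patient (10 with 10 infused) rest on comparison with not counting that patient as favourable. Against an observed-only percentage, a single affected patient in the n = 8 example makes a difference of 62.5 − 57.1 = 5.4 points. How many patients are affected is an assumption. The consequence is a distorted descriptive percentage on a secondary endpoint, worth correcting because the correction is cheap.

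**What to change.** In SAP 9.1, set this order of classification for each measure and timeframe:

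1. Any patient with a recorded threshold change is improved or worsened under the existing rule, including its precedence for improvement.
2. Stability/no change is assigned only if the patient has a baseline value and a value at the end of the timeframe (24-hour visit or Day-6 visit) and crossed neither threshold.
3. All remaining patients go into one of two mutually exclusive rows: died before end of timeframe with no threshold change recorded; or not assessable (withdrawn or missing).

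Add both rows to Tables 14.2.1.1 and 14.2.1.2. Keep them in the Safety Population denominator, do not count them as stable or improved, and show the observed-only percentage alongside.

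The cost is a few sentences and two rows, with no new data. The favourable percentage may be slightly lower. A patient with flat counts to Day 5 who misses Day 6 becomes not assessable for that timeframe; the observed-only figure shows how much such cases matter.

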### 1.9.2.2 Additional Hemostatic Therapy: All Cohorts

This product is not expected to increase the platelet corrected count increment (CCI). The infusion of platelets for six hours prior and one hour after infusion of Thrombosomes is

restricted. However, at any time, if the patient's clinical bleeding remains unchanged or deteriorates with additional or worsening bleeding, the patient's physician(s) may transfuse the patient with blood products, hemostatic agents, or coagulation factors without limitation. The study patient will be followed for safety data for 30 (+2) days post-infusion of the dose of Thrombosomes.

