-  Blood products may include packed red blood cells, whole blood, apheresis platelets, pooled whole blood derived platelets, cryoprecipitate, and plasma. In the event of a blood product transfusion occurring after Thrombosomes infusion on Days 1-6, CBC results will be required from a blood sample collected within 8 hours prior to transfusion and within 1 hour (+30 min) following transfusion.
-  Hematology CBC analytes will include WBC, RBC, hemoglobin, hematocrit, platelets, MPV, neutrophils, lymphocytes, monocytes, eosinophils, and basophils. Daily CBC will be required, but all CBC data for each patient during hospitalization through Day 6 will be collected.
-  During screening, coagulation testing will include only PT/INR, aPTT, D-dimer, and fibrinogen. At and following baseline, testing will include PT/INR, aPTT, D-dimer, fibrinogen, TAT, PF 1+2, TEG or ROTEM, and TGA. For baseline testing, PT/INR, aPTT, D-dimer and fibrinogen will be collected no more than 8 hours prior to infusion.
-  EKG measures include only heart rate and QT interval with Fridericia's correction. The EKG will be repeated if performed more than 4 days before infusion.
-  For each of the time-points that require archive samples, 2 10-mL samples will be drawn (1 for plasma and 1 for serum).
-  Medications may include but will not be limited to over-the-counter remedies, herbal preparations, vitamins, supplements and intravenous fluids.
-  Vital signs will include heart rate, respiratory rate, systolic and diastolic blood pressure, and body temperature.
-  Routine chemistry will include Na, K, Cl, CO2, glucose, BUN, creatinine, albumin, total bilirubin, Ca, AST, alkaline phosphatase, ALT, GGT, LDH, total cholesterol, and total protein. Special chemistry will include hs Troponin I and hs Troponin T.

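### SAP 9.1 has no rule for blood counts taken after a transfusion, so a rise produced by transfusion is tabulated as clinical improvement and can remove a patient from the worsening row

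*SAP*

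**What the plan says.** SAP 9.1 produces Tables 14.2.1.1 (Safety Population) and 14.2.1.2 (Evaluable Population). Each patient goes into one of three rows for each of hemoglobin, hematocrit and platelets, over two timeframes (infusion to 24 hours, infusion to Day 6). The thresholds are 1 g/dL, 3% and 5,000/µL, up or down. On which readings count: "For each patient, categorization will require consideration of all measurements recorded across all time-points within the timeframe". On conflict: "When both improved conditions and worsened conditions have been distinctly observed at different time-points, the patient will fall into the category of clinical improvement". A patient who crosses neither threshold is stable by default.

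SAP 2.2.2 defines the endpoint as patients who "show either stability (i.e., no change) or an intermittent or sustained change toward clinical improvement in hematology measures". SAP 2.1.2 gives its use, within and across dose cohorts: "Post-infusion patterns showing stability or change toward clinical improvement in hematology measures will be used as preliminary indicators of possible product efficacy".

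Protocol 1.9.2.2 says that when bleeding is unchanged or worse the physician "may transfuse the patient with blood products, hemostatic agents, or coagulation factors without limitation". The same section does not anticipate a rise in the platelet corrected count increment from the product. Footnote 6 to SAP Table 2 adds a requirement for post-infusion transfusions through Day 6, in these words: "CBC results will be required from a blood sample collected within 8 hours prior to transfusion and within 1 hour (+30 min) following transfusion".

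No section supplies a post-transfusion rule for these tables. SAP 6.2 leaves it open whether unscheduled readings enter summaries. SAP 6.5 plans no stratified or adjusted analysis. The transfusion subgroups of SAP 6.6 are used for the plots in SAP 8.3, not for the 9.1 tables. SAP 9.2 tabulates transfusions separately.

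**The concern.** Transfusion may follow a lack of benefit, since the protocol permits it when bleeding has not improved. A transfusion also raises the count that 9.1 measures. The two rules together allow a patient whose count fell, and who was then transfused, to be shown as improved and to disappear from the worsening row. For platelets, the protocol itself gives no reason to expect a rise from the product.

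At stake is the reading of the improvement and worsening percentages as a preliminary efficacy signal, including the comparison across dose cohorts. Part of any difference between cohorts could reflect transfusion practice. Type I error is not at stake, because no test is attached to these tables.

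**Working it through.** **No figure to reproduce.** The sample size was not statistically derived (SAP 4), and the documents give no expected category rate, transfusion rate or transfusion increment. The document inputs are 8 patients per cohort, the ±5,000/µL platelet thresholds, the reading times and the tie rule. All other inputs below are assumptions, and only platelets were modelled.

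**Step 1: direction within one patient.** Fix the patient's course. A transfusion that raises the matching count can add a reading at or above baseline + 5,000 and can remove a reading at or below baseline − 5,000. It cannot do the reverse. Under the tie rule the patient can therefore enter improvement or leave worsening, but not the opposite. The scheduled 6 h, 24 h and Day 6 CBCs can pick up the rise (also Days 3–5, if the patient is hospitalized), so this does not depend on the extra CBCs taken around a transfusion.

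**Step 2: closed form.** Let *a* and *w* be the improved and worsened shares without transfusion, *t* the share transfused, and *q* the chance that a post-transfusion reading reaches the upper threshold, unrelated to the patient's category otherwise.

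- Improvement = a + (1 − a)·t·q
- Worsening = w·(1 − t·q)

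Take a = 0.10, w = 0.50, q = 0.8, per 8 patients:

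- t = 0: improvement 8 × 0.10 = 0.8; worsening 8 × 0.50 = 4.0
- t = 0.5: improvement 8 × (0.10 + 0.90 × 0.40) = 3.7; worsening 8 × 0.50 × 0.60 = 2.4
- t = 1: improvement 8 × (0.10 + 0.90 × 0.80) = 6.6; worsening 8 × 0.50 × 0.20 = 0.8

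**Step 3: simulation with no product effect.** 400,000 patients; serially correlated counts (correlation 0.7, SD 4,000/µL); transfusion increment with mean 10,000–20,000/µL and SD 8,000, seen at one reading only; Day 6 timeframe. Ranges run over the mean increment.

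- Model 1: four CBCs (1 h, 6 h, 24 h, Day 6), no drift, transfusion at random between 6 h and 24 h.
- Model 2: inpatients with seven CBCs, drift −1,000/µL per day, transfusion only after a reading 5,000/µL or more below baseline, given to none, half or all who reach that point.

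| | Transfused | Improved | Worsened | Stable or improved | Both thresholds met |
|---|---|---|---|---|---|
| Model 1 | 0 of 8 | 26% | 25% | 75% | 0.4% |
| | 4 of 8 | 50–60% | 14–19% | 81–86% | 6–10% |
| | 6 of 8 | 62–78% | 8–16% | 84–92% | 9–15% |
| Model 2 | 0% | 22% | 58% | 42% | 5% |
| | 41% | 37–54% | 27–43% | 57–73% | 20–37% |
| | 55% | 43–65% | 16–37% | 63–84% | 27–48% |

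The tie rule's share depends on the model. In Model 2 with half treated, improvement rises by 15.3–31.6 points and the both-thresholds share by 15.4–31.8, so almost all of the rise passes through the tie rule. In Model 1 with 4 of 8 transfused, the corresponding rises are 23.9–34.7 and 5.7–9.7 points, so most of it does not.

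**Step 4: between cohorts.** A separate simulation (reading SD 2,000, mean increment 10,000) let the clinical course differ. Per 8 patients, drift −1,000 per day with 27% transfused gives improvement 1.9 and worsening 4.1. Drift −4,000 per day with 47% transfused gives 1.7 and 6.3. Here the more heavily transfused cohort looks worse.

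**The case against.** *Counting a temporary rise is deliberate.* This stands. SAP 2.2.2 accepts intermittent change. A reader might infer that the tie rule is itself the mistake, but the documents support it as a stated choice. What that choice does not cover is crediting the product with a rise that follows a transfusion.

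*A more transfused cohort may simply be sicker.* This also stands. A reader might infer that the improvement row must rank cohorts by their transfusion rate. Step 4 shows otherwise, and the protocol links transfusion to bleeding that has not improved.

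*Transfusion is already reported.* In part. SAP 9.2 and the listings disclose it, but they are not linked to the 9.1 categories. The subgroup plots cover hemoglobin and platelets but not hematocrit. Their transfusion windows close 1 hour (platelets) or 24 hours (other products) after infusion, well short of Day 6.

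*Unscheduled CBCs may be excluded under SAP 6.2.* Possibly, but scheduled readings after a transfusion remain.

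*The effect is small at 8 per cohort.* This is fair for the combined endpoint in Model 1: from 0 to 4 of 8 transfused, stable-or-improved moves by 8 × (0.807 − 0.749) = 0.5 to 8 × (0.859 − 0.749) = 0.9 patient. The improvement row moves more, by 8 × (0.495 − 0.256) = 1.9 to 8 × (0.603 − 0.256) = 2.8 patients.

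**Conclusion.** The gap is real and should be closed. As written, 9.1 attributes transfused rises to the product and lets them cancel earlier falls. For a given clinical course the bias runs one way: improvement up, worsening down. Across cohorts with different courses the direction is not guaranteed.

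The size cannot be established from the documents. The figures above are illustrations for platelets on assumed increments, variability, drift and transfusion rates. Nothing was computed for hemoglobin or hematocrit, where the matching products are red cells and whole blood.

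A reader might infer that dose escalation is affected. The documents do not support that: the tables are descriptive and untested, and SAP Appendix 1 does not list them among the DMC outputs, although the DMC does receive a listing of selected hematology data. The consequence is limited to interpreting a secondary, preliminary efficacy table.

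**What to change.** In SAP 9.1 and Tables 14.2.1.1 and 14.2.1.2:

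1. State that a reading taken after a relevant transfusion (platelets for platelet count; red cells or whole blood for hemoglobin and hematocrit) cannot on its own qualify a patient as improved. Count transfusions from the baseline CBC sample, not from infusion, to the end of the timeframe. The baseline CBC may precede infusion by up to 2 hours, and the pre-infusion restriction in Protocol 1.9.2.2 names only platelets.
2. If the only threshold rise follows such a transfusion and a threshold fall came before it, count the patient under worsening, with a sub-row *then rose after transfusion*. If no fall came before it, use a separate row *rise only after transfusion*.
3. Patients with a fall and a rise not preceded by transfusion may stay under improvement, shown as a sub-row.
4. Give the stable-or-improved total both without and with the *rise only after transfusion* row, as a lower and an upper figure.
5. State whether unscheduled CBCs enter the classification.

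Item 2 is needed because one separate row taking precedence over all others would leave worsening uncorrected. In a re-run of Model 2 (increment 20,000), worsening was 60%, 28% and 16% both as written and with such a row. Counting earlier falls as worsening holds it at 60%. In Model 1 it gives 19–23%, against 24% without transfusion in that re-run. Cutting off readings at the first transfusion is no substitute: in the Step 4 simulation (drift −1,000), going from 0% to 95% transfused, worsening falls from 5.1 to 1.1 per 8 and stability rises from 2.3 to 6.5.

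Item 4 is needed because exclusion alone overshoots. In the Model 1 re-run the lower total drops from 76% to 33–53%. The upper total, 100% minus worsening, is 77–81%.

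The cost is SAP text and programming, since the transfusion and CBC data are already collected. The downsides are small cells with 8 per cohort, a less favourable improvement percentage, and a row defined by a post-infusion event that the product might influence, so it should be read descriptively. A stable result supported by transfusion is not corrected.

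A separate minor point: SAP 8.3 omits hemoglobin, hematocrit and platelets from the change-from-baseline summary (Table 14.3.5.2), although Protocol 1.16 plans it for every laboratory test. Adding them would not cure the transfusion problem.
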